3.1.1 Screening/Run-in Period (Up to 4 weeks)

The purpose of the Screening/Run-in Period is to ensure that all enrolled subjects are on stable doses of baseline medications, do not have “white coat” hypertension, can demonstrate proper and reliable use of the BP monitoring device prior to study drug treatment, and meet all study inclusion/exclusion criteria.

The Screening/Run-in Period will consist of four Screening Visits (S1, S2, S3, and S4) that are approximately 7 days (at least 4 days but no more than 10 days) after the prior screening Visit (Appendix A).

Visit S1: Each subject will be issued a HBP monitor and provided with training on device use. Subjects will be instructed to measure HBP in triplicate twice daily after Visit S1 (Section 7.3.2.1).

Visits S2, S3 and S4: Two types of office BP measurements will be performed before other scheduled activities (except for S4 where the EQ-5D-5L will be the first assessment). Both measurements will be performed with the subject alone after 5 minutes of seated rest (Section 7.3.2.2):

1. Performed by an automatic oscillometric BP monitoring device that can measure BP in triplicate (automated Office BP, AOBP)
2. Performed by the subject using their issued HBP monitoring device in triplicate (subject-measured BP, SMBP)

Note: Study staff should not be present while both office BP measurements are being performed. Subjects will be instructed to bring their issued HBP device to every visit.

To be eligible for this study, subjects will be required to meet all of the following criteria (see Section 4 for complete criteria):

1. AOBP SBP 135 to 160 mmHg at each Screening Visit; however, AOBP SBP may be < 135 mmHg at either S2 or S3 Visits
2. eGFR of $25 - \leq 45$ mL/min/1.73 m² (mean [calculated by the Interactive Web Response System – IWRS] of two values measured at S1 and S3 (or 7 to 28 days apart) during the Screening/Run-in Period)
3. Local laboratory measurements of K⁺ level of 4.3 – 5.1 mEq/L obtained at Visits S1, S3 and S4 (all measurements must be within range)
4. Does not meet any exclusion criteria

If hemolysis of the local sample is detected or suspected (see Section 7.1.1) at Screening Visits (S1 and S3), a repeat of the potassium measurement from a separate blood draw will be performed within 1 day. If the repeated potassium level does not meet entry criteria, then the subject is considered a Screen Failure.

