3.1.2 Double-Blind Treatment Period (12 weeks)

Randomization (Baseline – Day 0) Visit:

Subjects who meet all eligibility criteria at Visit S4 will be randomized on the same day to either patiromer or placebo treatment (1:1) with stratification based on the local potassium level at Visit S4 ($4.3 - < 4.7$ or $4.7 - 5.1$ mEq/L) and history of Type 1 or 2 diabetes mellitus (Yes or No). The S4 assessments will become the baseline assessments. A combined visit (S4/Randomization [Baseline/Day 0]) will be recorded for all randomized subjects.

All randomized subjects will be provided with detailed instructions for when to take spironolactone, patiromer/placebo, and other baseline medications after considering the subject's current medication regimen, patiromer/placebo instructions regarding administration, and subject preference (see Section 5.5.1). The subject will be instructed to begin taking study drugs (spironolactone and patiromer/placebo) on the following day (Day 1) and on the morning of their subsequent study visits to delay taking their blood pressure medications until office blood pressure measurements have been completed.

Treatment Period Visits (refer to Appendix A):

During the Double-Blind Treatment Period, study visits will occur at Week 1 (Day 8 ± 3 days), Week 2 (Day 15 ± 3 days), Week 3 (Day 22 ± 3 days), Week 4 (Day 29 ± 3 days), Week 6 (Day 43 ± 7 days), Week 8 (Day 57 ± 7 days), Week 10 (Day 71 ± 7 days), and Week 12 (Day 85 ± 7 days).

Patiromer/placebo treatment:

Patiromer/placebo will be taken at a starting dose of two packets once daily (QD). Based upon the treatment algorithm, patiromer/placebo will be increased in two-packet per day increments for local $K^+ > 5.1$ mEq/L in intervals of at least 1 week up to a maximum dose of six packets QD. For subjects with $K^+ < 4.0$ mEq/L, patiromer/placebo dose will be decreased by at least two packets per day. The minimum dose of patiromer/placebo is 0 packets. Patiromer/placebo should be taken with food, at least 3 hours before or 3 hours after administration of other concomitant medications including spironolactone. Refer to Appendix B for complete dosing and monitoring instructions.

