4.1 Inclusion Criteria

Eligible subjects must meet all the following criteria:

1. Provide written informed consent prior to participation in the study
2. Age \geq 18 years
3. Taking at least three antihypertensive medications, one of which is a diuretic, for at least 28 days at a stable dose. ACE inhibitors or ARBs should be included among these three antihypertensive medications, unless previously not tolerated or contraindicated.
4. Uncontrolled hypertension as documented by AOBP SBP 135 to 160 mmHg at each Screening Visit; however, AOBP SBP may be $<$ 135 mmHg at either S2 or S3 Visits (see Section 7.3.2.2)
5. eGFR of 25 – \leq 45 mL/min/1.73 m² (mean [calculated by the IWRS] of two values measured at S1 and S3 or 7 to 28 days apart during the Screening/Run-in and calculated using CKD Epidemiology Collaboration [CKD-EPI] formula)
6. Qualifying local laboratory K⁺ measurements of 4.3 – 5.1 mEq/L obtained at Visits S1, S3 and S4 (all measurements must be within range)
7. Females of child-bearing potential must be non-lactating, must have a negative serum pregnancy test at screening, must use a medically acceptable form of birth control from 28 days prior to screening through the study and for 28 days after completion of the study

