2. AOBP
3. SMBP
4. Other procedures

6.1 Screening/Run-in Period (up to 4 Weeks):

Before any study-specific procedures are performed, the subject will receive an explanation of all study procedures and must sign and date a written informed consent form (ICF) approved by an institutional review board (IRB) (see Section 12.2 for additional requirements). The timing of the Screening Visit (and all subsequent visits) must take into account planned absences at the research facility and the need for study visits according to the Schedule of Events (Appendix A).

The subjects will be instructed to arrive at the scheduled time for each Screening Visit to allow for completion of all assessments including measurement of the potassium level by the local laboratory. At the first Screening Visit, subjects will be assigned a unique subject identification number, which will be generated during Screening Visit registration in IWRS. On the morning of all study visits after S1, the subjects will be instructed to delay taking their BP medications until office BP measurements have been completed.

The Screening/Run-in Period will consist of 4 Screening Visits (S1, S2, S3, and S4) that will occur approximately 7 days (at least 4 days but no more than 10 days) after the prior Screening Visit (Appendix A).

6.1.1 S1

The following activities will be performed (Appendix A):

- Subject signs informed consent

- IWRS registration
- Review inclusion and exclusion criteria
- Collect demographic information
- Review medical history
- Measure height and weight
- Measure resting heart rate (pulse) after the subject has been sitting quietly for 5 minutes
- Perform physical examination
- Perform 12-lead ECG
- Record AOBP (Section 7.3.2.2) performed using automatic oscillometric office device with the capability of performing automatic multiple measurements after the study staff has left the room (unwitnessed measurement after the subject has been sitting quietly for 5 minutes)
- Issue HBP monitor and appropriate size blood pressure cuff
- Train subject on use of HBP monitor and collection of twice daily measurements (see Section 7.3.2.1)
- Collect blood samples for evaluation of (see Appendix E):
 - Potassium level (measured locally and by central laboratory)
 - Serum chemistry including creatinine, eGFR (central laboratory)
 - Hematology (central laboratory)
 - Pregnancy (central laboratory)
- Collect urine sample for urinalysis (central laboratory)
- Dietary counselling

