6.4 Key Considerations for Blood Pressure

Blood pressure is measured in three ways in this study:

- AOBP: Automated Office Blood Pressure
- SMBP: Subject-Measured Blood Pressure (performed at the study site using the HBP monitor)
- 7dHBP: 7-day Home Blood Pressure

The AOBP is an unwitnessed measurement taken at the clinic using an automatic office device that collects 3 measures of SBP/DBP. The mean of the three values is used for titration of study medication, and is the value that will be used for most analyses.

The SMBP is an unwitnessed measurement taken at the clinic using the subject's home blood pressure device. The home blood pressure device takes 3 readings automatically, and the mean of the three is used. If an AOBP is unavailable at a visit, for whatever reason, the SMBP will be used in its place to determine titration of study medications.

The HBP device is used by the subject outside the clinic to take measurements twice a day. At each sitting, 3 readings are taken automatically and uploaded to the Bioclinica database. The 7-day home blood pressure (7dHBP) is calculated from these measurements as follows:

1. Morning average = average of all measurements with time stamp midnight to before noon on given day
2. Evening average = average of all measurements with time stamp noon to before midnight on given day
3. Daily average = average of morning and evening averages
4. 7-day HBP (7dHBP) = average of daily averages for prior 7 days

The morning/evening averages include all values within the specified timeframes. If there are no valid readings during the morning time period, the morning average is missing, and the daily average will be based on the available values during the evening period, and similarly if there are no valid readings in the evening period. If there are no valid readings in either the morning or evening period, the daily average will be missing for that day. The 7dHBP is calculated using as many daily averages as are available for the previous 7 days. A valid 7dHBP requires that there be, at an absolute minimum, at least one valid reading for each of the prior 3 days. Readings taken with the HBP device while at the clinic are excluded from the calculation of the 7dHBP. Because the calculation requires averages of averages, rounding should not be done until the final 7dHBP result has been calculated.

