8.9.2 Secondary Efficacy Analysis

The secondary efficacy endpoint is change from Baseline in AOBP SBP at Week 12 or last available AOBP SBP on or prior to the first date of addition of any new BP medications or increases from any baseline BP medications.

Baseline AOBP is defined as the latest available AOBP on or before the date of first dose date.

Changes/additions to baseline BP medications are recorded on the Antihypertensive Medications eCRF. The earliest date of any recorded increase/addition will be compared to the date of the Week 12 AOBP, and the rules below will be applied. Note that only dates of BP medication increases/additions with start date on or before the upper limit of the Week 12 window will be considered.

- If the earliest date of BP medication increase/addition is on or after the date of the Week 12 AOBP, or there is no record of any increase/addition, the Week 12 AOBP SBP will be used for analysis.
- If the earliest date of BP medication increase/addition is prior to the Week 12 AOBP, or when the Week 12 visit should have occurred if there is no Week 12 AOBP, then the AOBP on or before and closest to the earliest date of change will be used for analysis.
- If a subject has no Week 12 AOBP and no record of any BP medication changes/additions, the subject will not be included in this analysis.

In above rules, the SMBP, if available, may be used in place of a missing AOBP at the same visit.

The secondary efficacy endpoint will be analyzed using an analysis of covariance (ANCOVA) model, with baseline AOBP SBP as a continuous covariate and factors for treatment group, baseline serum potassium (K^+ 4.3 – < 4.7 or 4.7 – 5.1 mEq/L), and Type 1 or 2 diabetes mellitus (Yes or No).

The analysis will be performed using the ITT and PP Populations. A sensitivity analysis will be performed using the last observation carried forward, when a subject has no Week 12 AOBP and no record of any BP medication changes/additions.

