8.9.3.1 Blood Pressure

Change in AOBP SBP from baseline to Week 12

Treatment groups will be compared for change in AOBP SBP at Week 12 regardless of increase in antihypertensives by using both ANCOVA and repeated measures methods.

An ANCOVA analysis will be carried out using a model that includes baseline AOBP SBP as a continuous covariate and factors for treatment group, baseline serum potassium (K^+ 4.3 to < 4.7 or 4.7 to 5.1 mEq/L), and Type 1 or diabetes mellitus (Yes or No). This analysis will include only ITT subjects who have AOBP SBP (or SMBP if AOBP is missing) at both Baseline and Week 12.

In addition, a repeated measures mixed model analysis will be performed using all ITT subjects who have an AOBP SBP (or SMBP if AOBP is missing) assessment at Baseline and at least one post-baseline assessment at Week 1 or later. The model will include baseline AOBP SBP as a continuous covariate and factors for treatment group, time, baseline serum potassium (K^+ 4.3 to < 4.7 or 4.7 to 5.1 mEq/L), and Type 1 or 2 diabetes mellitus (Yes or No).

AOBP over time

Summaries of AOBP SBP/DBP will be provided at each visit and for change from Baseline, by treatment group. SMBP SBP/DBP may be used for missing AOBP SBP/DBP. Summaries of change at each post-baseline time point will include only subjects who have non-missing values at baseline and at the post-baseline time point of interest.

Mean SBP/DBP and mean change from baseline will be presented graphically.

The change from Baseline in AOBP SBP over time prior to the first date of addition of any new BP medications or increases from any baseline BP medications will also be presented for the subjects who remained on spironolactone through Week 12.

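### The three Week 12 SBP models adjust for AOBP from one screening visit and leave comparable S2 and S3 values unused, at a modest cost in precision

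*SAP*

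**What the plan says.** SAP 8.9.2 defines the baseline for the secondary endpoint: "Baseline AOBP is defined as the latest available AOBP on or before the date of first dose date". Protocol 3.1.2 fixes which visit that is: "The S4 assessments will become the baseline assessments". One AOBP value is an average over three automated measurements within a visit (SAP 6.4): "The mean of the three values is used for titration of study medication, and is the value that will be used for most analyses".

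Three models use it. The secondary ANCOVA is fitted "with baseline AOBP SBP as a continuous covariate and factors for treatment group, baseline serum potassium" and diabetes status. The Week 12 ANCOVA in SAP 8.9.3.1 has the same terms. For the repeated measures analysis in that section, "The model will include baseline AOBP SBP as a continuous covariate and factors for treatment group, time, baseline serum potassium" and diabetes status.

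Earlier AOBP values exist. Protocol 3.1.1 describes the procedure: "Visits S2, S3 and S4: Two types of office BP measurements will be performed before other scheduled activities", with the EQ-5D-5L coming first at S4. Both types are taken with the subject alone after five minutes of seated rest. Medication timing is set in Protocol 6.1: "On the morning of all study visits after S1, the subjects will be instructed to delay taking their BP medications". S2, S3, S4 and Week 12 therefore share that instruction, and S1 does not.

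Entry restricts the values (Protocol 4.1): "Uncontrolled hypertension as documented by AOBP SBP 135 to 160 mmHg at each Screening Visit", except that S2 or S3 may be below 135. The SAP does not say why S2 and S3 stay out of the models.

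**The concern.** A baseline covariate helps an ANCOVA to the extent that it predicts the outcome. One visit's AOBP is a mixture of the subject's usual level and visit-to-visit variation. Averaging three measurements within the visit reduces within-visit noise but leaves the variation between visits. The entry rule also confines S4 to a 25 mmHg band, which narrows the true differences between subjects that the covariate is meant to capture. S4 alone is therefore likely to be a weak predictor of Week 12 SBP, and S2 and S3 carry further information on the usual level.

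At stake is the width of the confidence interval for the SBP difference. Improved blood pressure control is one of the two stated objectives (Protocol 2, SAP 2.1), and the plan states no power for it.

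**Working it through.** **The plan's own figure.** The only sample size calculation is for the primary endpoint: 280 subjects, 90% power, a 20-point difference, alpha 0.05. Base rates are not given. Assuming 40% versus 60%, the two-proportion formula gives (1.960 × √0.50 + 1.282 × √0.48)² / 0.20² = 129.3, so 130 per arm and 260 in all. With continuity correction it gives 140 per arm, 280 in all, as stated. This figure says nothing about SBP; 280 serves below only as a yardstick.

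**Without the entry rule.** Let r be the correlation of one baseline visit with the outcome and ρ the correlation between baseline visits. Adjusting for the mean of k visits leaves a residual variance fraction of

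1 − k·r² / (1 + (k − 1)·ρ).

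At r = ρ = 0.5, k = 1 leaves 0.750 and k = 3 leaves 1 − 0.75/2 = 0.625, a cut of 1 − 0.625/0.750 = 16.7%. Over ρ from 0.3 to 0.8 and r from 0.3 to 0.6 (r ≤ ρ), the cut runs from 1.5% to 20.5%. The entry rule compresses the baseline values, so these figures are too generous for this trial.

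**With the entry rule.** The rule was simulated as S1 and S4 within 135-160, S2 and S3 at most 160, and S2 and S3 not both below 135. Each visit value is the subject's usual level plus visit noise. The Week 12 value adds fresh visit noise and a subject-specific response. All SDs, and the screening-population mean of 140 or 148 mmHg, are assumptions. The comparison is S4 alone against S4 plus the mean of S2 and S3; averaging S2, S3 and S4 into one covariate gave the same result.

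Conversions for a variance cut c:
- equivalent extra subjects = 280/(1 − c) − 280
- narrowing of the interval = 1 − √(1 − c)
- half-width = 1.96 × residual SD × √(2/140)

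| Between-subject / visit / response SD (mmHg) | Residual SD, S4 only → with S2-S3 | Variance cut | Extra subjects | 95% CI half-width (mmHg) | CI narrower by |
|---|---|---|---|---|---|
| 8 / 12 / 8 | 15.41 → 15.24 | 2.2% | 6 | 3.61 → 3.57 | 1.1% |
| 10 / 10 / 8 | 13.90 → 13.60 | 4.2% | 12 | 3.26 → 3.19 | 2.1% |
| 12 / 8 / 8 | 12.41 → 12.02 | 6.2% | 19 | 2.91 → 2.81 | 3.1% |
| 15 / 8 / 0 | 9.57 → 9.00 | 11.5% | 36 | 2.24 → 2.11 | 5.9% |

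Variance cuts come from unrounded SDs. The first row uses a screening mean of 148, the others 140; the choice hardly matters.

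The last row assumes that every subject responds identically, so it is an outer bound. With between-subject SD 8-12, visit SD 7-11 and response SD 5-8, the cut is about 2.6-10%, or 280/0.974 − 280 ≈ 7 to 280/0.90 − 280 ≈ 31 subjects. With response SD 12 it is about 2-4.5%.

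In the 10 / 10 / 8 setting the SD of S4 falls from √(10² + 10²) = 14.1 in the screened population to 6.61 among those who qualify. S4 then correlates only 0.14 with Week 12. It removes 1 − (13.90/14.04)² = 2.0% of the outcome variance, less than the further 4.2% that S2 and S3 remove.

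The simulation covers a Week 12 ANCOVA. The repeated measures model was not simulated separately.

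**The case against.** The case for leaving the SAP alone is a fair one. S4 is the protocol's designated baseline and agrees with the general last-value rule in SAP 6.3.3. It is the only screening visit where the EQ-5D-5L precedes AOBP, as at Week 12 (Protocol 6). The value is already a mean of three unattended measurements. Every SD above is assumed, and response may vary more than 5-8 mmHg, because Week 12 mixes subjects on 50 mg, on 25 mg and off spironolactone. The practical gain is small: for an illustrative 5 mmHg difference in the 10 / 10 / 8 setting, power moves from 0.853 to 0.868.

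All of this stands as a limit on size. It does not remove the gain, because the fix keeps S4 as the baseline and adds to it. Diet counselling or device training could shift mean SBP during screening, but a shift common to all subjects does no harm to a covariate. Uneven drift would only reduce the benefit.

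Three stronger readings are tempting, and the documents do not support them.

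- A reader might infer that the planned ANCOVA is biased or invalid. It is neither: adjusting for one pre-randomization value is sound.
- A reader might take the secondary endpoint as the only blood pressure comparison with a stated test. SAP 8.9.3.1 also compares the groups on Week 12 SBP, by two methods, and SAP 8.1 sets two-sided 0.05 for all tests.
- A reader might multiply the 20-point design difference by the 8.7 mmHg fall quoted in Protocol 1 (0.20 × 8.7 = 1.74) and say that the plan implies an effect below 2 mmHg. The plan states no SBP effect. The 8.7 mmHg is a home SBP reduction from a trial that the protocol places among studies largely limited to normal or mildly impaired renal function.

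**Conclusion.** The point holds as a modest, avoidable loss of precision in three SBP models. It is optional to act on: no conclusion becomes invalid, and the primary endpoint is unaffected. The direction is secure, since the gain was positive in every setting tried and an informative pre-randomization covariate cannot raise residual variance in large samples beyond the one degree of freedom it uses.

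The size is not secure. About 2-10% of residual variance is a reasonable range under the entry rule, and the lower half is more likely if response differs widely between subjects. The range depends wholly on assumed SDs and on S2 and S3 predicting Week 12 about as well as S4 does.

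**What to change.** Before unblinding, amend SAP 8.9.2 and 8.9.3.1 so that the secondary ANCOVA, the Week 12 ANCOVA and the repeated measures model each include the mean of the available S2 and S3 AOBP SBP values as a second continuous covariate beside S4. Keep S4 as the baseline for the change score, so that the endpoint is unchanged. Leave S1 out, because the delayed-medication instruction begins only after it. Say that the SMBP substitution in SAP 7.2 applies to a missing S2 or S3 value. Carry the covariate into the per-protocol, last-observation and subgroup runs of the 8.9.2 model so that they stay comparable.

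The cost is SAP wording and one degree of freedom. The data are already collected before randomization and are needed for eligibility, so few values should be missing.

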For subjects on spironolactone 25 mg QD (before Week 3), spironolactone may be increased to 50 mg QD before the Week 3 Visit for persistent SBP ≥ 180 mmHg (assessed by AOBP), at the investigator's discretion. For subjects on spironolactone 50 mg QD, additional BP medication may be added to control persistent SBP ≥ 165 mmHg (assessed by AOBP) at the discretion of the investigator. This decision may reflect the degree of blood pressure elevation, the time since last spironolactone dose adjustment, and the level of urgency to lower blood pressure, in the investigator's judgment. Baseline medication doses should not be changed except for AE-related reasons where changes to baseline medications can be justified by the Investigator (e.g., increases in loop diuretics for new edematous states or discontinuation of baseline medication for drug-related AEs).

For all subjects (on or off spironolactone) with AOBP ≥ 200 mmHg, subjects should be treated in accordance with the standard of care for BP management and the Investigator's judgment (i.e., additional medications or change in baseline medication dose are permitted, Appendix D).

Note: All subjects will remain in the study and complete all study assessments in accordance with the protocol.

Unscheduled Visits:

For subjects with study drug (spironolactone or patiromer/placebo) modifications based on BP assessments or potassium levels, an Unscheduled Visit should be conducted within 1 week after this modification unless the next scheduled visit is within 1 week of the study drug modification, in which case the subject will return at the next scheduled visit.

Upon completion of all Double-Blind Treatment Period assessments at the Week 12 Visit (or ET Visit), subjects will discontinue all study drugs that they are receiving (patiromer/placebo/spironolactone). After study drug discontinuation, the treatment of hypertension should proceed in accordance with the standard of care for BP management and the Investigator's judgment.

3.1.3 Follow-up Visit (2 Weeks after Week 12 or ET Visit + up to 7 day window)

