9.6 Efficacy Analyses

9.6.1 *Primary Efficacy*

The proportion of subjects remaining on spironolactone at Week 12 will be compared between treatment groups (spironolactone/patiromer versus spironolactone/placebo) using the Cochran-Mantel-Haenszel test, stratified by baseline potassium category (4.3 to < 4.7 mEq/L or 4.7 to 5.1 mEq/L). Additionally, a sensitivity analysis will include stratification by study site (small sites will be pooled).

The primary efficacy analysis will be performed using the ITT Population.

Subjects who terminate from the study early or discontinue study spironolactone early, for any reason, will be considered as not having remained on spironolactone.

9.6.2 *Secondary Efficacy*

The secondary efficacy variable for this study is change from Baseline in AOBP SBP at Week 12 or last available assessment prior to addition of any new BP medications or changes to any baseline BP medications.

The secondary efficacy endpoint will be analyzed using an analysis of covariance (ANCOVA) model, with baseline AOBP SBP as a covariate and baseline serum potassium as a categorical factor (K^+ 4.3 – < 4.7 or 4.7 – 5.1 mEq/L). The analysis will use the ITT Population.

9.6.3 *Other Endpoints*

Additional end-points will be compared between treatment groups including (please refer to the statistical analysis plan for further information):

- Change in AOBP SBP from Baseline to Week 12
- Potassium levels over time (measured both centrally and locally)

- Proportion of subjects with serum $K^+ \geq 5.5$ mEq/L
- Average daily dose and cumulative dose of spironolactone
- Time to discontinuation of spironolactone
- Change from baseline to Week 12 in albuminuria (ACR)
- EQ-5D-5L questionnaire results at Baseline and at Week 12/ET

Change in AOBP at Week 12 will be analyzed with an ANCOVA model using the BPA Population. Additionally, change at Week 12 will be analyzed using a repeated measures mixed model that will include all ITT subjects with at least one measurement of AOBP SBP at Week 1 or later. Models will include baseline AOBP SBP as a covariate and baseline serum potassium as a categorical factor (K^+ 4.3 – < 4.7 or 4.7 – 5.1 mEq/L).

Potassium levels will be summarized for local and central values at each time point. Counts (%) of subjects who have experienced no potassium measurement ≥ 5.5 mEq/L will be presented at each time point.

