1 INTRODUCTION

This document presents the statistical analysis plan (SAP) for protocol RLY5016-207, entitled “A Randomized, Double-Blind, Placebo-controlled, Parallel Group Study of Patiromer for the Enablement of Spironolactone Use for Blood Pressure Control in Patients with Resistant Hypertension and Chronic Kidney Disease: Evaluation of Safety and Efficacy (AMBER)”.

Results obtained from the analyses outlined in this document will provide the basis of the Clinical Study Report (CSR) for this study. The statistical rationale and analysis methods specified in this document take precedence over those described in the protocol, should there be any differences.

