5 ANALYSIS SETS

5.1 Intent-to-treat Population (ITT)

The Intent-to-Treat (ITT) Population includes all subjects who have been randomized and have taken at least one dose of spironolactone and at least one dose of patiromer/placebo.

All efficacy analyses will be performed on the ITT population, analyzed by planned treatment group assignment. In addition, the primary and secondary endpoints will also be performed using the Per-protocol Population.

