6.1.2 Secondary Efficacy Endpoint

The secondary efficacy endpoint is change from Baseline in AOBP SBP at Week 12 or last available AOBP SBP prior to addition of any new BP medications or increase from any baseline BP medications.

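### SAP 8.5 leaves antihypertensives started after the last study dose out of the medication tables, and mixed terms in SAP 8.9.2 leave two small groups with no secondary-endpoint rule (minor)

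*SAP*

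**What the plan says.** **Medication tables.** SAP 8.5 calls a drug *prior* if it starts before the first dose. It introduces concomitant drugs as those used in the study period, then narrows this to drugs that start by the last study dose and have not ended before the first. The antihypertensive summaries are a subset of that class, and the listings cover only the two classes. Protocol 9.6.5.4 promises summaries of use during the study, and Protocol 5.5 collects medications until the Follow-up visit or call. Under Protocol 3.1.2, patiromer/placebo stops with spironolactone and the subject stays on study. Appendix D then allows BP drugs to be added up to Week 12.

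**Secondary endpoint.** Protocol 9.6.2 uses Week 12 or the "last available assessment prior to addition of any new BP medications or changes to any baseline BP medications". SAP 6.1.2 uses Week 12 or the "last available AOBP SBP prior to addition of any new BP medications or increase from any baseline BP medications". SAP 1 says that its methods "take precedence over those described in the protocol, should there be any differences".

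SAP 8.9.2 then gives three rules, with the subject-measured reading (SMBP) allowed in place of a missing AOBP at the same visit:
- Bullet 1: if the first increase or addition is on or after the Week 12 reading, or "there is no record of any increase/addition, the Week 12 AOBP SBP will be used for analysis".
- Bullet 2: if an increase or addition came before the Week 12 reading (or before that visit was due, if there is no reading), the AOBP closest to and not after it is used.
- Bullet 3: for a subject with "no Week 12 AOBP and no record of any BP medication changes/additions, the subject will not be included in this analysis".

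The section adds: "A sensitivity analysis will be performed using the last observation carried forward, when a subject has no Week 12 AOBP". That sentence goes on to require, like bullet 3, that no change or addition is on record.

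**The concern.** Subjects who stop study drug early are those in whom in-trial rescue BP treatment is most likely, and the trial expects more of them on placebo. An antihypertensive table by arm that leaves out drugs started after the stop would understate rescue use, probably more in that arm.

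For the endpoint, a pre-specified rule should give every subject either a value or a stated exclusion. Bullets 1 and 2 ask about increases and additions; bullet 3 and the LOCF condition ask about changes and additions. Reducing or stopping a baseline drug is a change but not an increase, and the protocol foresees it: section 3.1.2 permits "discontinuation of baseline medication for drug-related AEs". Nor does 8.9.2 say whether an early-termination (ET) AOBP counts as Week 12, although other SAP sections write Week 12/ET and Protocol 6.4 performs the Week 12 assessments at that visit. This is the only secondary endpoint and it carries the BP objective.

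**Working it through.** **1. The plan's own figure.** The only design number is 280 subjects (140 per arm) for a 20-point difference with 90% power. No control rate is stated. At an assumed 40% v 60%, two-sided 0.05, the usual formula gives 260 without and 280 with continuity correction, so the figure reproduces. Nothing below changes it.

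**2. SAP 8.5 on example dates (first dose Day 1).**
- BP drug started Day 20, last study dose Day 85: 20 ≤ 85, so concomitant.
- BP drug started Day 40, last study dose Day 29: 40 > 29, so not concomitant; 40 > 1, so not prior. It appears in neither class.

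The number of such starts is unknown. At the planned effect there are 0.20 × 140 = 28 more stoppers on placebo. That is the pool on which the omission falls unequally, not a count of omitted drugs. The secondary endpoint takes its dates from the Antihypertensive Medications eCRF, so it is unaffected.

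**3. SAP 8.9.2 when Week 12 AOBP and SMBP are both missing.**

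| BP-drug record | Bullet 1 | Bullet 2 | Bullet 3 and LOCF | Result |
|---|---|---|---|---|
| Increase/addition before Week 12 was due | no | applies | no | earlier AOBP used |
| None | points to an absent reading | no | apply | excluded; LOCF only |
| Reduction or stop only | points to an absent reading | no | not met: a change is on record | no value anywhere |
| Increase/addition after Week 12 was due, within the window | compares with an absent date | no | not met: an addition or change is on record | no value anywhere |

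If *changes* is read loosely as *increases*, the third row joins the second. The fourth row stays empty on either reading. If the due date is Day 85, the window of ± 7 days ends on Day 92, so the fourth row covers roughly Days 85 to 92.

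**4. Protocol and SAP cut-offs.** For a subject with a Week 12 reading and only a reduction or stop, the SAP uses Week 12, whereas the protocol's words would use the last reading before the change. As a scale, Protocol 1.2 expects the BP difference to follow the difference in retention: 0.20 × 8.7 = 1.74 mmHg. The 8.7 is from Protocol 1: home SBP, in a trial largely limited to normal or mildly impaired renal function. If one BP drug is worth 8.7 − 4.2 = 4.5 mmHg and the arms differ by an assumed 2 to 10 points in reductions or stops, the shift is 0.02 × 4.5 = 0.09 to 0.10 × 4.5 = 0.45 mmHg, in either direction.

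**5. Would LOCF be a better main analysis?** Let p be retention and L the assumed share of stoppers who leave with no BP-drug change and no Week 12 reading. With exclusion, the share on spironolactone among those analysed is p/(1 − (1 − p)L). With LOCF, if leavers' last readings are on drug, it is p + (1 − p)L, and the contrast between arms is 20 × (1 − L) points.

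| L | Exclusion, 40 v 60% | 60 v 80% | 70 v 90% | LOCF, last reading on drug |
|---|---|---|---|---|
| 5% | 19.99 | 19.58 | 19.39 | 19 |
| 10% | 19.95 | 19.13 | 18.74 | 18 |
| 25% | 19.61 | 17.54 | 16.63 | 15 |

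Example: 0.7/(1 − 0.3 × 0.25) = 75.7% and 0.9/(1 − 0.1 × 0.25) = 92.3%, a contrast of 16.63. At 8.7 mmHg, exclusion loses 0.00 to 0.29 mmHg; LOCF on these terms loses 0.01 × 8.7 = 0.09 to 0.05 × 8.7 = 0.44 mmHg, more than exclusion in all nine cells. If leavers' last readings were all off drug, LOCF would give the full 20 points.

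**The case against.** The strongest reply is that 8.9.2 is a wording slip. Bullet 2 itself speaks of a date of change when it means an increase or addition, so the terms were probably used interchangeably; the reduction-only subject would then be excluded and restored by LOCF. SMBP substitution and the effort to retain everyone to Week 12 make the affected groups small. This stands as to size, but a programmer still has to guess, and the loose reading does not close the last row of the table.

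On 8.5, the closing words about a missing end date could be read as a separate route into the class. Ongoing drugs would then count, and only those started after the last dose and already ended would be missed. That is not the natural reading, and it still leaves a gap.

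Two stronger readings are tempting.

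- A reader might infer that the main analysis breaks the intention-to-treat promise ("All efficacy analyses will be performed on the ITT population"), because of two subjects with the same readings one is kept and the other dropped according to a BP-drug decision. The documents do not support this. Both define the endpoint as the pre-addition reading once a drug is added. Bullet 2 applies that definition; bullet 3 handles a missing Week 12 value, which Protocol 9.7 leaves to the SAP, and LOCF is pre-specified. The repeated-measures model in SAP 8.9.3.1 also uses the dropped subjects' post-baseline readings, though for Week 12 change regardless of added drugs.
- A reader might infer that the SAP's narrower cut-off is an unresolved conflict. Both documents give the SAP precedence. What is missing is an explanation.

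**Conclusion.** Two points hold. SAP 8.5 is wrong as written, because in-trial antihypertensives started after an early study-drug stop fall outside both medication classes, contrary to its own opening description and to Protocol 9.6.5.4. SAP 8.9.2 is internally inconsistent: on its wording, two kinds of subject without a Week 12 reading get no value in the main analysis and no place in the LOCF analysis. The change from *changes* to *increases* is operative but unexplained.

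The severity is minor. The documents give no rates of missing Week 12 readings, BP-drug reductions or later additions, so no bias can be computed. The fractions of 1 mmHg shown above rest on assumed rates and on an effect from a different population. It might also seem to follow that LOCF should become the main analysis; step 5 shows that this is a trade-off that can go either way. Study drugs stop only after the ET assessments (Protocol 3.1.2), so a leaver's last reading may well be on spironolactone.

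**What to change.** **SAP 8.5.** Define concomitant as any medication taken from first dose through the Week 12 or ET visit, whether or not study drug has stopped. Tabulate antihypertensive starts by arm, before and after early study-drug stop. Report starts after Week 12/ET through Follow-up separately: everyone stops study drug by then and may receive standard-of-care treatment (Protocol 3.1.2 and 6.2.3), so pooling them would mix post-trial prescribing with in-trial rescue.

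**SAP 8.9.2.** Use *increase/addition* in all three bullets and in the LOCF condition. That puts the reduction-only subject under bullet 3 and LOCF. The single term does not cure the late-increase case, so also limit bullet 3 and the LOCF condition to increases or additions dated before Week 12 was due, and state that due date. State that an ET AOBP is not a Week 12 value, and whether it may be the carried-forward one. Add a sentence explaining why the protocol's cut-off was narrowed, and a sensitivity analysis that uses the protocol's cut-off.

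Keep the available-case ANCOVA as the main analysis and LOCF as sensitivity. A mixed model on AOBPs before any BP-drug change may be added as a further sensitivity analysis.

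**Cost.** SAP wording, one or two extra tables and one or two extra model runs, with no new data and no change in sample size.
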